10.0 Procedures Involved

Once a subject has been identified, the initial visit will be scheduled.

During the visit:

- 1. Informed consent will be completed
- 2. Record the patient's general medical history and habitual contact lens information, including lens design, power, and diameter.
- 3. An investigator will conduct visual acuity assessments of both eyes (Snellen).
- 4. Assess the fit of the PROSE device via slit lamp assessment of both eyes.
- 5. Assess the cornea and conjunctiva of both eyes with the PROSE device on and off.
- 6. Measure corneal intraocular pressure of both eyes after PROSE device removal
- 7. The investigator will instill one drop of topical anesthetic in both eyes followed by a lubricating preservative-free artificial tear drop, such as Refresh Plus, prior to IOP measurements.
- 8. Measure intraocular pressure of both eyes with the PD on via (method depends on which cohort the subject is in):
 - a. Scleral TonoPen
 - b. Scleral pneumatonometry
 - c. Transpalpebral Diaton
- 9. Reassess the ocular surface of both eyes after intraocular pressure measurement at the slit lamp biomicroscope with and without fluorescein staining in order to rule out adverse events, such as conjunctival abrasion or erosion or other irritations.

Procedure	Length of Time	Frequency of Repetition
	Required for	

Informed consent & HIPAA	20 minutes	Once
General History and Medications	10 minutes	Once
Visual Acuity	2 minutes	Once
Slit-lamp Examination (with PD)	4 minutes	Once
Corneal IOP Measurement (TonoPen)	5 minutes	Once
IOP Measurement (One of the below will be completed)		
COHORT 1: Scleral TonoPen		5 (maximum)
COHORT 2: Scleral Pneumatonometer	20 minutes	10 (maximum)
COHORT 3: Transpalpebral Diaton		5 (maximum)
Slit-lamp Examination after measurement	4 minutes	Once
TOTAL TIME	65 minutes	

The testing descriptions are summarized in the table below:

Test	Description
General History	Participants will be asked questions about their general, ocular and
and Medications	medication use histories along with contact lens use history if applicable.
Lens Evaluation	The PROSE device fit and vision will be evaluated.
Visual Acuity	The participant's vision in each eye while wearing lenses will be measured with a high contrast visual acuity chart. The participant will be asked to cover one eye and read the chart, and this procedure will be repeated for the other eye.
Slit-lamp	The participant's front portion of each eye and contact lenses will be
Examination	examined with a lighted microscope. The participant will be asked to
	place his/her chin on the chinrest and place his/her forehead against
	the bar and look straight ahead. The instrument's light will be shined
	onto the eye to visualize the ocular surface for approximately 4
	minutes per eye. Photographs will be taken at the discretion of the investigator.

Sodium Fluorescein	Sodium fluorescein staining will be used to evaluate ocular surface
	damage indicated by cell damage or death. Corneal and conjunctival
	staining will be scored using the Oxford grading scale.
Diaton tonometry	The Diaton device will be placed on the superior lid as the participant
	looks down to measure the intraocular pressure transpalpebrally.
Pneumatonometry	One drop of topical anesthetic (Proparacaine) will be instilled into
	each eye. The pneumatonometer will be placed on the superotemporal
	sclera and overlying conjunctival tissue as the participant looks down
	and in to measure the intraocular pressure.
Scleral TonoPen	One drop of topical anesthetic (Proparacaine) will be instilled into
	each eye. The participant will look down and in as the TonoPen probe
	lightly contacts the superior temporal sclera and overlying
	conjunctival tissue.
Corneal TonoPen	One drop of topical anesthetic (Proparacaine) will be instilled into
	each eye. The participant will look straight ahead and a probe will
	lightly contact the cornea to measure the intraocular pressure.

Table 3. Descriptions of tests

The following data will be collected in this study:

- Intraocular pressure via several different methods
 - Corneal TonoPen
 - Scleral TonoPen
 - Scleral pneumatonometry
 - Transpalpebral Diaton

11.0 Setting

Subjects will be asked to complete the study visits, which will be conducted in clinical facilities at BostonSight.

12.0 Drugs or Devices

The PROSE device is considered a class II medical device by the FDA. All rigid lens materials are FDA approved for use in a rigid contact lens, and they are not investigative devices.

All devices included in the study are standard of care, are intended to be used to measure intraocular pressure in clinical practice, and are FDA approved to do so. The Diaton was created to allow IOP measurement without contact with the ocular structures as the instrument touches only the outer part of the upper eyelid. The TonoPen and the pneumatonometer are typically used on the cornea but include an option of scleral measurement when corneal pathology or post-surgical conditions contraindicate corneal contact. There is literature supporting use of the pneumatonometer on the sclera for IOP measurement.⁴⁻⁸ Literature supporting use of the TonoPen on the sclera for IOP measurement is also available.^{4,9}

13.0 Risks to Subjects

TITLE: Tonometry Precision and Accuracy in PROSE Scleral Lens Wear: A Pilot Study PROTOCOL NUMBER: BFS-KR-IOP-02 DATE: 04/14/2020

This study presents a minimal risk to subjects. Risk with PROSE devices are those that are already associated with wearing any form of contact lens. All contact lens wearers are at risk for developing an abrasion ('cut' on the eye) during lens application or removal as well as inflammatory and/or infectious complications during lens wear, but there is no added risk by participating in this study. Measurement of IOP via conjunctival/scleral contact does introduce the risk of conjunctival abrasions, irritation, redness, or discomfort.

If a subject experiences an adverse event during the duration of the study, they will be instructed to call the study coordinator who will communicate with the investigators to determine the best course of action. If the subject needs to be seen due to an adverse event, a study investigator will examine them and the customary procedure for management will be followed.

If an adverse event such as an abrasion occurs during a study visit, the condition will be treated as it is customarily, and the fees associated with treatment will be covered by the study. Additionally the subjects are encouraged to call immediately if experiencing any pain or other discomfort after the exam, which may be an indicator of irritation following intraocular pressure measurements.

In a review of current literature, no reported adverse events or serious adverse events were found ifor each specific manner of IOP measurement with the instruments to be used in this study (scleral TonoPen, scleral pneumatonometry, Diaton). No documented adverse events for these instruments were found in literature at the time of submission.

If, in the unlikely event, during the study a patient experiences any serious adverse event, they will be removed from the study and the IRB will be notified.

14.0 Potential Benefits to Subjects

There may be no benefit to the subject for participation in this study.

15.0 Withdrawal of Subjects

Subjects will be withdrawn from the study if they are unable to complete the tasks in the study protocol. In addition, if they experience an adverse event in which the investigator does not feel that the subjects should continue, they will be withdrawn.

The data from a subject that withdraws or is terminated from the study will not be included in the analysis.

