5.0 Number of Subjects

A minimum of 30 subjects will be enrolled in this study with 10 subjects in each of the three cohorts. This is a low risk study. We can expect an approximate 10% drop-out rate, so we will expect to recruit approximately 33 subjects; and the first 30 to be eligible and complete the study will be used for data analysis.

The first 10 subjects that are eligible to proceed and consented will be consecutively enrolled in the first cohort (scleral TonoPen). The second 10 subjects that are eligible to proceed and consented will be consecutively enrolled in the second cohort (scleral pneumatonometry). The third 10 subjects that are eligible to proceed and consented will be consecutively enrolled in the third cohort (Diaton). Sequential assignment allows for focus on one instrument and one technique at a time by one investigator.

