9.0 Study Endpoints

The study design allows for the subjects to serve as their own control. The subjects' baseline IOP will be measured with the standard clinical approach via corneal TonoPen. Corneal TonoPen was chosen as the control method for intraocular pressure measurements as it is a standard of care method and process used every day in clinical practice by ophthalmologists and optometrists. This will be compared to the IOP measurement obtained in the same subject with lenses in place.

The primary endpoints in this study are as follows:

- 1. Intraocular pressure
 - a. TonoPen, corneal without lens
 - i. Baseline, one measurement
 - b. TonoPen, scleral with lens
 - i. IOP and confidence level will be recorded
 - ii. Attempt 5 measurements maximum
 - Goal of achieving 3 measurements in total with confidence level of 90% of higher
 - iii. One measurement defined as a completed result or attempting to measure until the machine times out
 - c. Pneumatonometer, scleral with lens
 - i. Measurement in "manual IOP mode"
 - ii. IOP and standard deviation (SD) will be recorded for each measurement
 - iii. Attempt 10 measurements maximum
 - Goal of achieving 3 measurements in total with a SD of 2 mmHg or less
 - iv. One measurement defined as a completed result or attempting to measure until the machines times out
 - d. Diaton, transpalpebral with lens

- i. Up to 6 individual attempts are included in each complete measurement, with the instrument averaging the measurements for a result
- ii. Reliable average is confirmed:
 - When the instrument shows symbol <> and the mean IOP value is non-flickering
 - When the instrument shows symbol <> and the mean IOP value is flickering with a result of equal or less than 19 mmHg
- iii. Attempt 5 complete measurements maximum
 - Goal of achieving 3 reliable measurements
 - Reliability defined (per manufacturer Diaton, Ryazan State Instrument-Making Enterprise, www.diaton-tonometer.com) as:
 - a. +/- 2mmHg error in range 5-20mmHg
 - b. +/- 10% error in range 20-60mmHg

Correct calibration of each instrument will be ensured prior to the study per individual manufacturer's standards. The first measurement of every subject will not be included but will serve as one practice measurement to familiarize the subject with the measurement process.

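### Section 15 discards all data of withdrawn subjects and Section 5 analyses completers only, so a tonometer's own early failures can drop out of its results

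*Protocol*

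**What the plan says.** Section 15.0 gives two grounds for withdrawal. The first is general: "Subjects will be withdrawn from the study if they are unable to complete the tasks in the study protocol". The second is an adverse event after which the investigator judges that the subject should not go on. Section 13.0 adds removal after any serious adverse event. Section 15.0 then sets the consequence for the data, with no reason exempted: "The data from a subject that withdraws or is terminated from the study will not be included in the analysis".

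Section 5.0 limits the analysis in the same way: "the first 30 to be eligible and complete the study will be used for data analysis". It plans for the loss by over-recruiting: "We can expect an approximate 10% drop-out rate, so we will expect to recruit approximately 33 subjects". Cohorts of 10 are filled one after another, in order of eligibility and consent.

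Section 10.0, step 8, is the test measurement: "Measure intraocular pressure of both eyes with the PD on via" the cohort's method. Section 13.0 links that step to harm: "Measurement of IOP via conjunctival/scleral contact does introduce the risk of conjunctival abrasions, irritation, redness, or discomfort".

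Section 9.0 bears on what completing means. For the TonoPen it reads "Goal of achieving 3 measurements in total with confidence level of 90% of higher", within at most 5 attempts. The pneumatonometer (at most 10) and the Diaton (at most 5) have goals of the same form. For the TonoPen and pneumatonometer, an attempt that runs to time-out counts as a measurement. The Diaton has no such sentence.

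**The concern.** The study exists to describe how well three tonometers work over a scleral lens, and Section 1.0 says the results are to inform choices for a full study. In that setting, failure to finish a measurement, or stopping because it was not tolerated, is information about the instrument. The protocol treats it as a reason to remove the subject.

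Two things are lost. Valid readings taken before the stop are discarded, and subjects stopped part-way may well be the harder ones to measure. The subject also leaves the denominator, so the results show no failure. Either can make a method look better than it is when the full study chooses among methods.

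This is a rule that the protocol states in two sections, so it is not a detail left to an analysis plan.

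**Working it through.** **1. The plan's own figure.** Inputs from Section 5.0: 30 completers and about 10% drop-out. 30 × 1.10 = 33; 30 / (1 − 0.10) = 33.3. The stated figure of about 33 is reproduced. It means that roughly 3 recruits are expected not to reach the analysis. Section 5.0 does not say whether they are lost before or during the test measurement.

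**2. What a subject has to complete.** Times from the Section 10.0 table: 20 + 10 + 2 + 4 + 5 + 20 + 4 = 65 minutes. After the 20 minutes of consent, 45 remain, of which 20 (20/45 = 44%) are the test tonometry. There is one visit, so inability to complete is largely inability to complete this step.

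**3. Which subjects are clearly lost.** Setting Sections 9.0, 10.0, 13.0 and 15.0 side by side:
- *Uses all attempts, fewer than three acceptable readings.* Section 9.0 implies that the task is complete, so the data stay. No sentence says so.
- *Stopped during step 8 for intolerance or an adverse event, or unable to go on.* Withdrawn under Section 15.0; all data are dropped, including the corneal baseline and any valid test readings.
- *Adverse event found at step 9.* The readings are already taken. They are lost only if the subject is then withdrawn or removed.
- *One eye measurable, the other not.* Step 8 asks for both eyes. Section 15.0 does not say whether this counts as inability to complete.

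**4. What the rule can hide.** The protocol gives no failure rate, so the counts here are assumptions. Suppose a cohort reaches 10 completers after x subjects were excluded because of the measurement. The non-completion rate among those attempted is x/(10 + x), with exact (Clopper-Pearson) 95% intervals:

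| x | Among all attempted | As analysed |
|---|---|---|
| 0 | 0/10 (0 to 30.8%) | 0/10 (0 to 30.8%) |
| 1 | 1/11 = 9.1% (0.2 to 41.3%) | 0/10 (0 to 30.8%) |
| 2 | 2/12 = 16.7% (2.1 to 48.4%) | 0/10 (0 to 30.8%) |
| 3 | 3/13 = 23.1% (5.0 to 53.8%) | 0/10 (0 to 30.8%) |

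The last row places all of the roughly 3 planned drop-outs in one cohort and attributes them all to the measurement. It is an extreme case.

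**5. How easily one subject is affected.** With an assumed measurement-related non-completion rate f, the chance that at least one of 10 subjects is excluded is 1 − (1 − f)^10. For f = 5%, 10%, 20% and 30% this is 40%, 65%, 89% and 97%.

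Steps 4 and 5 concern completion. They do not measure bias in precision or accuracy, for which the protocol gives no basis.

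**The case against.** The strongest reply is that Section 9.0 already deals with ordinary failure. Attempts are capped for all three methods, three acceptable readings is only a goal, and time-outs count as measurements for two devices. A reader might infer from Section 15.0 that every subject without three acceptable readings is removed. The protocol does not support that, because on its natural reading such a subject has completed. This part of the objection stands and confines the clear loss mainly to subjects stopped during step 8.

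The adverse-event route is also narrow. Section 13.0 calls the risk minimal and reports no documented adverse events for these methods in the literature, and the planned safety check follows the measurements. Section 3.0 screens for adequate scleral exposure and for ability to complete the procedures. All of this limits how often the problem can arise. It does not change what happens to the data when it does.

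A reader might also infer that the two scleral cohorts are flattered relative to the Diaton, which Section 12.0 says touches only the eyelid. Unequal loss is possible, but nothing in the protocol sizes it. Nor can it be inferred that cohorts must end below 10, since Section 5.0 over-recruits.

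Finally, completion rate is not a listed endpoint, and a subject with no readings adds nothing to precision or accuracy under any rule. That is correct. For those two measures, the recoverable loss is partial data. The count of failures remains relevant to choosing a method for the full study.

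**Conclusion.** The point holds in a limited form. Sections 15.0 and 5.0 together fix a completers-only analysis that discards valid readings and leaves no trace of subjects stopped because the tested measurement failed or was not tolerated. The effect on precision and accuracy is possible, narrow and of unknown size. It is nil if nobody is stopped early. The figures in the working rest on assumed exclusion counts or rates. They show what would be hidden and do not estimate a bias.

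The conclusion rests on reading Section 9.0 as making a subject who uses all attempts a completer. If the sponsor intends otherwise, the problem is wider. It is worth correcting because the change is cheap and, with 10 subjects per cohort, each lost subject counts.

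**What to change.** Replace the last sentence of Section 15.0 and the completers-only rule in Section 5.0 with wording to this effect:

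> Every eligible, consented subject in whom the test tonometer was attempted is included in the assigned cohort. All valid readings after the practice measurement, from either eye, enter the precision and accuracy analysis, unless the subject withdraws permission to use the data. A subject who uses the permitted attempts without three acceptable readings has completed the task. Failure to obtain acceptable readings and early stopping are counted by cohort among all subjects attempted.

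Add to Section 5.0 that an attempted subject with no usable post-practice reading stays in the attempted denominator and may be replaced within the same cohort, so that 10 subjects per cohort have usable readings. The rules on when a subject is clinically withdrawn are unchanged.

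**Cost.** Mostly wording, and possibly a few more recruits. If a share s of recruits yields no usable reading (assumed equal across cohorts and independent between subjects), 30 usable subjects need 30/(1 − s) recruits on average. For s = 0, 5% and 10% this is 30, 31.6 and 33.3. The probability that 33 recruits suffice (negative binomial) is 1, 0.92 and 0.58; for 36 it is 1, 0.998 and 0.94.

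Reported precision, accuracy or success may look slightly less favourable. A subject with a single valid reading in an eye informs accuracy but not repeatability, so slightly fewer than 10 per cohort may contribute to the latter.

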16.0 Costs/Payments to Subjects

The only cost that the subjects may be responsible for in this study is the cost of transportation to and from the appointments.

Compensation will be given in \$20 gift card.

17.0 Compensation for Research-Related Injury

If there is an ocular injury in this study directly related to the use of the lenses or during IOP measurement, treatment for the injury and any subsequent referrals will be covered by the study. The subject will not receive any direct compensation. If there is an unrelated or non-ocular injury during a subject's enrollment in the study, it will not be covered by the study.

18.0 Confidentiality

The subject ID worksheet, informed consent, subject surveys, and examiner worksheets will all be kept in a single binder, locked in the office of the principal investigator. The informed consent forms and the subject ID worksheet will be kept in a separate binder from the study data. At the start of participation in the study, the subject will be assigned a non-identifiable subject ID that will be used for identification on all other documents used in the study. This identification document, which will be the only document that decodes the subject, will be kept in a locked filing bin in a locked room within BostonSight, separate from the informed consent and other study documents. Names, email addresses, and telephone numbers will be recorded in this subject ID worksheet, which will be a paper file kept in the locked office of the principal investigator.

All other exam findings will be recorded on the paper forms and stored in a binder. This binder will be kept locked in the principal investigator's office when not being used to add or remove data collection worksheets.

Only the investigators will have access to the paper and electronic records kept in this study.

All study data will be stored for a minimum of 3 years following study completion. The link will be maintained to allow pertinent regulatory or government agencies to inspect the data and ensure that subjects participated in the study. The principal investigator will be responsible for maintaining study data security and subject confidentiality.

19.0 Provisions to Protect the Privacy Interests of Subjects

We will ensure that all data is maintained with confidentiality and will assure subjects of this when they begin the study. If subjects are not comfortable with disclosing any of the information that is asked in the study, they will not be pressured to disclose, but they may not be able to participate if the withholding prevents us from screening or determining eligibility in the study. All PHI (DOB, name, health information) will be stored in the locked office of the Principal Investigator.

Subjects will only be asked questions that are relevant to the study and their ocular health. The investigators, who are all optometrists that regularly see patients and communicate about potentially sensitive information, have been trained to develop proper rapport with patients and study subjects. All investigators will make every effort to avoid seeming intrusive when asking the subjects questions.

20.0 Informed Consent Process

Informed consent will be obtained before any testing is done. The subject will be provided an informed consent document written in non-technical language. The study staff will review the document with the subject and will give the subject adequate time to review the form and ask any questions before deciding whether to participate. After answering any questions, if the study staff believes the subject comprehends the elements of the informed consent document, the study staff will invite the subject to participate in the study and will have the subject sign the consent form. The investigators and key personnel associated with the informed consent process are trained to not influence the participant in their decision to participate in the research or not. The individual may choose not to sign the consent form without any coercion from the study personnel. Non-participation in the study from patients will not impact future care. Informed consent is estimated to take approximately 20 minutes for this study.

